2.1.1.2. Secondary Endpoint

The secondary objective of this study is to evaluate the overall safety data on 3 mg/mL Gablofen® (baclofen injection) given by the intrathecal route of administration.

2.1.2. Safety and Tolerability Endpoints

Safety will be evaluated by the incidence of treatment emergent AEs and by changes in the physical examination findings and vital signs to the end of the treatment period. Adverse events will be coded to preferred term and system organ class using the Medical Dictionary for Regulatory Activities (MedDRA version 13.1). Also Medical History and Clinical evaluation for inflammatory mass formation will be included in the safety analysis.

The safety variables to be evaluated in this study are:

1. Adverse Event
2. Physical Exam
3. Vital Sign
4. Medical History
5. Clinical evaluation for inflammatory mass formation

These variables will be evaluated at the time points indicated in Schedule of Events in the protocol.

2.2. Statistical Hypotheses

No formal statistical hypotheses will be tested. Descriptive statistics will be used to assess safety and tolerability objectives.

3. STUDY DESIGN

This is a prospective twelve-month Phase IIIb clinical safety trial followed by 2-year, Phase IV study that will be conducted at 10 to 15 clinical trial sites that are experienced with the use of intrathecal baclofen. All subjects will be entered after signing an IRB approved informed consent. Subjects will be followed for the duration of their treatment with Gablofen® (baclofen injection) 3 mg/mL using the SynchroMed® II Programmable Pump or until the study is terminated. Subjects will be evaluated for clinical complications associated with the use of intrathecal baclofen that are considered signs and symptoms of an inflammatory granuloma, specifically new radicular pain at the level of the catheter tip, and/or spinal cord compression. Case report forms will be collected from the investigator at every clinical monitoring visit for the first 12 months for each subject enrolled and then every 6 months thereafter. If there are any signs or symptoms identified which may indicate an inflammatory granuloma formation, an MRI scan with and without infusion will be performed (with consent of the subject) to evaluate the potential presence of an inflammatory granuloma. Events that may be related to an inflammatory granuloma will be classified as definite granuloma, possible granuloma, or other catheter related problem (confirmed not caused by a granuloma) or other clinical sequelae caused by the underlying disease or infusion system related event. An interim analysis will be conducted when 100 subjects on the 3 mg/mL concentration of Gablofen® (baclofen injection) reach 9 months of treatment. Additionally, a second interim analysis will be completed after the first cohort of 100 subjects reach 12 months. Thereafter, annual safety reports will be generated as part of this 3 year program and a final study report completed when all subjects complete 36-months of treatment.

4. PLANNED ANALYSES

4.1. Interim Analysis

Two interim analyses will be conducted when 100 subjects reach nine (9) months of therapy and when 100 subjects reach twelve (12) months of therapy.

4.2. Final Analysis

The timing of the final analysis will be the end of the 36-month program. The final analysis will be completed following database freeze. Any changes from the planned analyses described in this section will be stated in the final study report.

5. SAMPLE SIZE CONSIDERATIONS

5.1. Sample Size Determination

Up to 150 subjects will be enrolled at up to fifteen investigative sites. The sample size for this study is not based on statistical considerations. The sample size was selected to ensure that 100 subjects will remain in the study for 12-months of evaluation.

5.2. Sample Size Re-estimation

A re-estimation of sample size will not be performed in this study.

6. ANALYSIS POPULATIONS

Safety Population

All subjects who were administered any amount of investigational product will be included in the analysis of safety.

Intent-to-treat (ITT) Population

The intent-to-treat (ITT) population will include subjects who were deemed eligible, have signed the informed-consent form (ICF) and treated with 3mg/ml baclofen.

Per-Protocol (PP) Population

The Per-Protocol population (PP) population will include subjects who were deemed eligible, signed the ICF, have been clinically evaluated for inflammatory granuloma formation through a physical examination evaluation of the investigator and receive therapy for at least 12 months and have no major protocol violations.

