2.1.1. Study Endpoints

2.1.1.1. Primary Endpoint

The primary endpoint is the rate of confirmed inflammatory granulomas after the first 12-months of therapy following the initiation of treatment with a 3 mg/mL formulation of Gablofen® (baclofen injection).

A confirmed inflammatory granuloma or mass is one where there are clinical signs and symptoms of an inflammatory granuloma, and an intradural extra-medullary mass is verified by an MRI with contrast enhancement. If only clinical signs and symptoms are identified, and no other assignable cause can be identified, the event will be recorded as a possible inflammatory mass.

All MRI-confirmed granulomas will be evaluated by a central independent radiologist as a routine trial procedure per the protocol.

Incidence is defined as the number of subjects with one or more events.

The rate of inflammatory granulomas will be evaluated based on 0 to 9 months, 0 to 12 months, and > 12 months of therapy.

For 0 to 9 months and 0 to 12 months of therapy, rate will be defined as:

$$\text{Rate} = I_T / (N_T + G_T)$$

Where:

I_T = Number of subjects with an inflammatory granuloma within the time interval

N_T = Number of subjects who reach the end of the time interval

G_T = Number of subjects with inflammatory granuloma who discontinue prior to reaching the end of the time interval

For > 12 months of therapy, rate will be defined as:

$$\text{Rate} = I_{>12} / N_{>12}$$

Where:

$I_{>12}$ = Number of subjects with an inflammatory granuloma after 12 months of therapy

$N_{>12}$ = Number of subjects who reach beyond 12 months of therapy

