10.3. Clinical Evaluation for Inflammatory Mass

The incidence (number of subjects with one or more events), frequency and rate of inflammatory granulomas will be summarized for 0 to 9 months, 0 to 12 months, and > 12 months of therapy. All inflammatory granulomas data will be listed for each subject and data from any SAE reports relating to inflammatory granulomas will be summarized in full detail.

A summary of the incidence and frequency of inflammatory granulomas by classification (Confirmed and possible) will also be presented.

These analyses will be performed for both the ITT and PP populations. The ITT population will be the primary analysis population.

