10.8. Statistical Method for Analysis of Safety and Demographic data

10.8.1. Wilcoxon Signed-rank Test

The Wilcoxon signed-rank test is a non-parametric statistical hypothesis test for the case of two related samples or repeated measurements on a single sample. It can be used as an alternative to the paired Student's *t*-test when the population cannot be assumed to be normally distributed. Like the paired or related sample *t*-test, the Wilcoxon test involves comparisons of differences between measurements, so it requires that the data are measured at an interval level of measurement. However, it does not require assumptions about the form of the distribution of the measurements. It should therefore be used whenever the distributional assumptions that underlie the *t*-test cannot be satisfied. This test will be used to test the difference between baseline and visit in case the variables are continuous. SAS code such as that below will be used to fit the method described above:

```
PROC UNIVARIATE;  
  VAR chage;  
  RUN;
```

10.8.2. 95% Confidence Interval

The incidence (number of subjects with one or more events) of inflammatory granulomas, suspected granulomas, and other catheter related events will be summarized and a 95% CI of the percent of subjects with one or more events will be presented. The rate of subjects with inflammatory granulomas for 0 to 9 months, 0 to 12 months and > 12 months therapy period will be summarized including a 95% CI of the mean rates. Results will be summarized in the three planned interim reports and included in the overall study final report at the end of 3 years.

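### The per-protocol set requires 12 months of therapy but is also used for the 0–9 month granuloma rate, so compliant subjects with 9 to under 12 months are left out at the first interim

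*SAP*

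**What the plan says.** - **PP membership.** SAP section 6 requires eligibility, consent and a clinical evaluation for granuloma, and that subjects "receive therapy for at least 12 months and have no major protocol violations". It makes no exception for any time window or interim.
- **Windows and populations.** SAP 10.3 states that the "rate of inflammatory granulomas will be summarized for 0 to 9 months, 0 to 12 months, and > 12 months of therapy", and then: "These analyses will be performed for both the ITT and PP populations. The ITT population will be the primary analysis population".
- **Denominator.** SAP 2.1.1.1 defines the rate for 0–9 and 0–12 months as I_T / (N_T + G_T). N_T is the "Number of subjects who reach the end of the time interval". G_T is the "Number of subjects with inflammatory granuloma who discontinue prior to reaching the end of the time interval".
- **Timing.** SAP 4.1: "Two interim analyses will be conducted when 100 subjects reach nine (9) months of therapy", and again when 100 reach 12 months.
- **Reporting.** SAP 10.8.2, after describing the rates and their 95% intervals: "Results will be summarized in the three planned interim reports" and in the final report. Protocol 14.3 also calls for a 9-month report.
- **The protocol's sets.** The evaluable population in the synopsis and in 14.3 has no 12-month requirement. Protocol 14.2 restricts the granuloma assessment to subjects who complete 12 months.

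**The concern.** A rate over the first 9 months, whose own denominator is the subjects who reach month 9, is to be computed in a set that needs 12 months for entry. At an interim timed by 9-month follow-up, the excluded subjects are not violators or early leavers. They are compliant subjects who have not yet been in the study long enough.

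The PP line printed beside ITT would therefore rest on a smaller, earliest-enrolled part of the 100. It would differ from ITT mainly because of calendar time, not adherence, and so would be a poor check on ITT. Because every PP member has 12 months of therapy, N_9 equals N_12 within PP at any data cut. The 0–9 month PP rate is then never a 9-month completer rate, even at the final analysis.

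**Working it through.** **The plan's own figure.** The only sample-size figures are up to 150 enrolled and 100 remaining at 12 months (SAP 5.1). The pair fits a one-third loss: 100 / (1 − 1/3) = 150. The SAP says the size is not statistically based, and no dropout rate is given, so there is no power calculation to reproduce.

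**Inputs from the documents.** 150 enrolled; first interim at 100 subjects with 9 months; PP needs 12 months; overall duration about 48 months (protocol synopsis), which with 36 months per subject suggests accrual over about 48 − 36 = 12 months.

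**Assumptions.** Uniform accrual over A months. No major violations. No dropout in the first set of figures.

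**Step 1: size of PP at the first interim.** The 100th subject is enrolled at 100A/150 months, so the cut-off is T = 9 + 100A/150. Subjects with at least 12 months by then number (150/A) × max(0, 100A/150 − 3), which is 100 − 450/A when positive.

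**Step 2: exact two-sided 95% upper limit for 0/n.** This is 1 − 0.025^(1/n). For n = 100 it is 3.6%.

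| Accrual A (months) | Cut-off T (month) | In PP, of the 100 | Left out | Upper limit for zero events in PP |
|---|---|---|---|---|
| 24 | 25 | 81.2 | 18.8 | 4.5% (0/81) |
| 18 | 21 | 75 | 25 | 4.8% (0/75) |
| 12 | 17 | 62.5 | 37.5 | 5.8% (0/62) |
| 9 | 15 | 50 | 50 | 7.1% (0/50) |
| 6 | 13 | 25 | 75 | 13.7% (0/25) |
| 4.5 or less | 12 or earlier | 0 | 100 | not defined |

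**Step 3: sensitivity to dropout.** Take exponential retention with two-thirds remaining at month 12, so retention at month 9 is (2/3)^(9/12) = 0.738. To have 100 at month 9, 100/0.738 = 135.5 must enrol. With A = 12, T = 9 + 135.5 × 12/150 = 19.84. By then 7.84 × 12.5 = 98 subjects were enrolled at least 12 months earlier, and 98 × 2/3 = 65 are in PP. The same calculation gives about 40 for A = 6 and about 78 for A = 24. Dropout changes the picture little at 12 months' accrual: 35 to 38 of the 100 are left out.

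**Step 4: later analyses.** Under the same dropout assumption, 150 × 0.738 ≈ 111 subjects reach month 9 and 100 reach month 12. The final PP 0–9 month rate would omit about 11 subjects who completed 9 months.

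**Step 5: what a corrected rule must also handle.** Protocol 3.3.1 has a subject with a detected granuloma discontinued. If that is followed, a case before month 12 cannot meet the 12-month rule, and G_T is zero in PP. One case at month 5, for example, gives ITT 1/(100 + 1) = 1.0% but PP 0/62. A rule that asked only for therapy through month 9 would still lose that case.

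**The case against.** - **ITT is primary and nothing is tested.** SAP 10.3 names ITT as primary and SAP 2.2 tests no hypothesis. No stopping rule or decision hangs on the PP rate. The ITT 0–9 month rate already has the right denominator. This stands, and it keeps the matter on a secondary line.
- **PP at the interim is inferred.** SAP 4.1 names no population, 10.3 names populations but not interims, and 10.8.2 names interim reports but not populations. Reading them together is natural, but no single sentence requires PP at the interim. If only ITT was meant there, the SAP should say so. The 0–9 month PP rate at the final analysis is affected either way.
- **Protocol 14.2 supports a 12-month rule.** It limits the granuloma assessment to 12-month completers, and the SAP rule may come from it. It does not fit a 9-month rate with a denominator of subjects reaching month 9, and the protocol's evaluable definition in 14.3 and the synopsis has no such rule. What stands is that the protocol sections must be reconciled too.
- **A reader might infer that the PP set will be empty at the first interim.** Without dropout, that needs the first 100 subjects enrolled within 3 months, about 33 a month across 10 to 15 sites. The approximate 48-month duration points to about 12 months' accrual and a PP set of about 62 to 65. Emptiness is the extreme case.
- **A reader might infer that the PP and ITT rates could not be compared.** In the 12-month case PP is 62 of the same 100 subjects. It is a subset with a wider interval, not an incomparable group.

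**Conclusion.** The mismatch is real and follows from the SAP's own rules: one 12-month entry rule is applied to a 9-month rate, and no section relaxes it. The effect on event-free subjects is mainly lost precision and an earliest-enrolled denominator. At the accrual implied by the 48-month duration, about 35 to 38 of the 100 are left out, and the upper limit for zero events rises from 3.6% to about 5.5% to 5.8%. Slower accrual is milder (about 81 of 100 and 4.5% over 24 months without dropout); faster accrual is worse (25 of 100 and 13.7% over 6 months).

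These sizes rest on assumed uniform accrual of 150 and on the assumed retention; the documents supply neither. The primary ITT result is not affected. The point merits a correction before the first interim, so that PP is not redefined after data have been seen.

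**What to change.** In SAP section 6, replace the single 12-month condition with one for each interval, leaving the other PP conditions as they are:

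- 0–9 months: therapy through month 9, or a granuloma within 0–9 months.
- 0–12 months: therapy through month 12, or a granuloma within 0–12 months.
- Over 12 months: therapy beyond month 12.

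The granuloma clause keeps the G_T cases in PP. State that the rule applies at both interims and at the final analysis, and name in SAP 4.1 the populations reported at each interim. Reconcile the rule with protocol 14.2, 14.3 and the synopsis, which differ on whether 12 months is required.

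On the stated assumptions, the 0–9 month PP denominator at the first interim would then be up to 100, less major violators, plus any early cases.

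Cost: short text changes in the SAP, one programming flag per interval and a cross-document reconciliation. No new data are needed.

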7. GENERAL CONSIDERATIONS FOR DATA ANALYSES

Data will be listed and summarized according to Social & Scientific Systems, Inc.'s reporting standards, where applicable.

Unless stated otherwise, descriptive summaries will include N , mean, standard deviation, median, minimum, and maximum for continuous variables and N and percent for categorical variables. For the change from baseline of continuous variables data, descriptive summaries will include N , mean, standard deviation, median, minimum, maximum, and p -value for the paired t-test or Wilcoxon signed-rank test (refer to section 10.8.1) between baseline and associated time point (p -values will be displayed only when

data is available for at least 10 subjects at that time point). Data will be summarized and reported. Version 9.1.3 or higher of the SAS™ system (SAS is a registered trademark of the SAS Institute, Inc., Cary, NC, USA) will be used to analyze the data as well as to generate tables, figures, and listings.

7.1. Multicenter Studies

Up to fifteen (15) investigative sites will participate in the study.

7.2. Other Strata and Covariates

There are no other strata and covariates.

7.3. Examination of Subgroups

A subgroup analysis will be performed for pediatric subjects and adult subjects. This will be done for the safety analyses of AEs, vitals, baseline physical examination, pump replacement, catheter replacement, and the incidence and rate of inflammatory granuloma.

8. DATA HANDLING CONVENTIONS

8.1. Premature Withdrawal and Missing Data

All subjects who withdraw from the study prematurely will be documented and the reason for their withdrawal will be reported in the final study report. Subjects who prematurely discontinue the study drug may be replaced. The study results up to the point of withdrawal for the withdrawn participant will be included in the data analysis. There is not any imputation method for missing data in this study.

8.2. Assessment Windows

Nominal times will be used for the descriptive summaries and plots of summary measures. Actual times will be used in the listings. Unscheduled screening and follow-up data will be excluded from statistical analyses. However, these data will be listed in the appropriate listings, summary tables, and summary plots.

8.3. Values of Clinical Concern

All changes in vital signs and abnormal values in physical examination and Clinical signs and symptoms that may indicate an inflammatory granuloma will be reviewed for clinical relevance by the Safety Review Team.

9. STUDY POPULATION

A Screening log of potential study candidates and an Enrollment log of subjects must be maintained at each study site. The general study population will consist of male and female subjects who are 4 years of age or older with severe spasticity and require intrathecal baclofen. Refer to the inclusion/exclusion criteria in the protocol for more detail.

9.1. Disposition of Subjects

Subjects will return to the clinic for safety evaluations and pump refills at least every 6 months or as dictated by their daily dose and need to refill the infusion pump. Subjects will also return at the nine (9) month time point for evaluations, even if the pump does not require refilling. Subjects who do not comply with the visit schedule will be discontinued from the study and pump refills continued with the approved concentrations of Gablofen® (baclofen injection). All data from enrolled subjects will be summarized to provide the number of subjects who complete the study treatment, and the number of subjects withdrawn, withdrawn due to AE, and withdrawn due to withdrawal of consent. Subject listing will be provided.

9.2. Protocol Deviations

Protocol deviations will be reported to Mallinckrodt Pharmaceuticals and will be documented in the clinical study report. Any changes from the analyses described within this statistical analysis plan will be stated in the final study report.

9.3. Demographic and Baseline Characteristics

Demographic and baseline characteristics for the subject population will be listed and summarized by using the safety population, ITT and PP populations.

9.4. Treatment Compliance

Study medication will be administered under the supervision of the study personnel. Compliance will be recorded in the case report form (CRF) at each visit (date and time of administration of study medication). Treatment compliance will be summarized and listed.

10. SAFETY ANALYSES

No formal statistical analysis of the safety data will be conducted. Safety data will be descriptively summarized by treatment and presented in a tabular and/or graphical form.

10.1. Extent of Exposure

The exposure data will be a by-subject listing, including refilled volume with the dates and times. Summary of treatment for mean of original daily dose and changed dose will also be provided.

10.2. Adverse Events

All adverse events (AEs) will be coded and classified according to System Organ Class (SOC) Preferred Term and Reported Term, using MedDRA. All AEs (non-serious and serious) will be listed. A summary of the number and percent of subjects reporting each event at least once will be generated for all AEs and also for drug-related AEs. Adverse events by SOC and Preferred Term will be summarized by severity. A listing of the relationship of AE body systems, group terms and verbatim text will also be produced.

10.3. Clinical Evaluation for Inflammatory Mass

The incidence (number of subjects with one or more events), frequency and rate of inflammatory granulomas will be summarized for 0 to 9 months, 0 to 12 months, and > 12 months of therapy. All inflammatory granulomas data will be listed for each subject and data from any SAE reports relating to inflammatory granulomas will be summarized in full detail.

A summary of the incidence and frequency of inflammatory granulomas by classification (Confirmed and possible) will also be presented.

These analyses will be performed for both the ITT and PP populations. The ITT population will be the primary analysis population.

10.4. Deaths and Serious Adverse Events

Any deaths and other serious adverse events will be summarized and listed as appropriate to the data.

10.5. Adverse Events Leading to Discontinuation of Investigational Product and/or Withdrawal from the Study and Other Significant Adverse Events

If any subject withdraws due to an AE, then a listing and a summary will be provided for these subject(s).

10.6. Pregnancies (as applicable)

Pregnancy test is not applicable for this study.

10.7. Other Safety Measures

10.7.1. Physical Examination

Baseline physical examination findings will be categorized by class variable (*i.e.*, normal or abnormal) and summarized by investigator determined body system. Clinically meaningful abnormalities found during physical examination (that were not present or have worsened since baseline) will be reported and analyzed as AEs.

10.7.2. Medical History

All medical history data will be listed for each subject.

10.7.3. Vital Signs

All vital sign data will be listed for each subject. A descriptive summary including change from baseline will be presented at the 6-month, 9-month, 12-month, and 36-month visits for the vital signs.

